The ACTH dosage chosen falls well within the range routinely employed, with efficacy, for treatment of MS relapses. It is known that this dose is well-tolerated, with an excellent safety profile. We have selected a 6-month treatment interval, which has become the standard phase II trial duration for multiple sclerosis therapeutic agents. This duration should also provide adequate time to study time of onset of effects of ACTH upon fatigue and whether they sustained over at least several months of medication use.

The primary endpoint of this study is a statistically significant reduction of fatigue in subjects who have RMS and fulfill the definition of PMSF when treated with ACTH compared to placebo. Known biological actions, both directly and indirectly, of ACTH upon the CNS make it a plausible candidate agent for the reduction of PMSF.

The secondary endpoints are: 1) statistically significant improvement in patient self-assessment of quality of life; 2) statistically significant reduction in patient self-assessment of depression; 3) statistically significant reduction in patient self-assessment of sleepiness measures when treated with ACTH, as compared to placebo, and 4) the safety and tolerability of twice weekly ACTH injections compared to placebo. The rationales for the secondary endpoints are: 1) the demonstration that quality of life improvements with ACTH use in patients with PMSF would increase the clinical significance or ACTH-induced reduction in PMSF; 2) fatigue and depression are so strongly correlated in patients with MS that reduction in depression with ACTH treatment would strengthen the possibility that depression and fatigue share, at least in part, a common mechanism, and a parallel decrease in depression would strengthen the validity of the potential causative action of ACTH upon fatigue; 3) sleepiness is strongly correlated with MS-induced fatigue and thus reduction in daytime sleepiness would be an additional measure of validity for ACTH-induced reduction in MS-induced fatigue; 4) ACTH use, although demonstrated to be safe in treating patients with MS, is being used on a twice-weekly basis over a 6 month period, which is a regimen that has not been previously employed, to our knowledge, in MS patients.

C. RESEARCH DESIGN AND METHODS

Study Design

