The proposed study is a 28-week randomized, placebo-controlled, double-blind trial comparing the efficacy of ACTH versus placebo for the treatment of fatigue in patients with RMS (RMS). Ninety patients with RMS who meet all of the eligibility criteria will be enrolled from five participating sites. Eligible patients will be consented by site investigators or delegated research personnel before undergoing any study procedures. Subjects will be randomized to ACTH or placebo at 1:1 ratio.

Endpoints

The primary objective of this study is to assess the efficacy of ACTH versus placebo in reducing fatigability in patients with relapsing MS. The primary endpoint is a statistically significant reduction of fatigue measured by MFIS and FSS, which will be administered at baseline, week 8, 16, 24, and 28.

Secondary objectives include assessment of the tolerability and safety of weekly ACTH treatment vs. placebo and evaluation of ACTH on depression, sleepiness, and quality of life measures and the correlations between measures. The secondary endpoints are measured by BDI-II, ESS, SF-36 at baseline, week 8, 16, 24, and 28. Clinical and laboratory adverse events (AE) and serious adverse events (SAE) will be monitored continuously during the study period to capture safety and tolerability information.

Patient Recruitment

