1. Patient has a relapse during the study. A relapse is defined as a new symptom, or worsening of pre-existing neurologic symptoms, of at least 24 hours duration, in patients who had been clinically stable for the prior 30 days, in the absence of fever, sleep deprivation or severe emotional stress.
2. Patient has an adverse event that presents unacceptable risk judged by the investigator
3. Patient has inadequate adherence to the protocol
4. Patient is lost to follow-up
5. Patient becomes pregnant

Treatment Overview**Dosage and Administration of Acthar® or matching placebo**

The study drug (ACTH 40 units or identical-appearing placebo) will be given subcutaneously twice weekly for 2 weeks. If the patient tolerates this dosage regimen, the dose will be increased to 80 units or placebo twice weekly. If the 80 unit dosage is not tolerated, the dosage will be reduced to 40 units twice weekly for the remainder of the 24 week participation. The weekly doses will be given 3 days apart, for example, on every Monday and Thursday or every Tuesday and Friday. Patients are not allowed to take doses on consecutive days. If a patient cannot take a dose on a scheduled day, the dose can be taken either a day early, or a day late. Patients that forget to take their scheduled dose will be encouraged to take their dose the following day.

Randomization/Treatment assignment and blinding

A total of 90 patients will be randomized either to active drug (ACTH), or placebo in a 1:1 ratio stratified by study site. Each study site will be assigned a site number, and each patient who signed consent form and received a screening test will have a unique study ID, which identifies the patient and the study site at which they participate throughout the study. Within each site, subjects will be randomized in blocks of 4, 2 ACTH and 2 placebo treated patients, to achieve balance in the allocation of subjects to study drug versus placebo arms. The order in which each of the 4 samples is selected will be predetermined by a

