The following clinical and laboratory evaluations will occur 16 weeks after baseline with a +/- 4 day window. The investigator/treating neurologist will review inclusion/exclusion criteria to confirm patient eligibility before study drug is dispensed.

- Interval medical and neurological history
- Vital signs
- Physical and neurological exam
- Laboratory assessments: CBC, Urinalysis, CMP, Pregnancy test/HCG (female only)
- MFIS, FSS, BDI-II, ESS, SF36, C-SSR*
- Study drug dispensing
- Protocol compliance study drug accountability
- Concomitant therapy and AEs
- Additional serum sample for research purposes

* The C-SSR must be reviewed by the site principal investigator or treating physician prior to the patient leaving the clinic

Visit 5/Week 24 (24 weeks +/- 4 days from baseline)

The following clinical and laboratory evaluations will occur 24 weeks after baseline with a +/- 4 day window. The investigator/treating neurologist will review inclusion/exclusion criteria to confirm patient eligibility.

- Interval medical and neurological history
- Vital signs
- Physical and neurological exam
- Laboratory assessments: CBC, Urinalysis, CMP, Pregnancy test/HCG (female only)
- MFIS, FSS, BDI-II, ESS, SF36, C-SSR*
- Protocol compliance study drug accountability
- Concomitant therapy and AEs

- Additional serum sample for research purposes

* The C-SSR must be reviewed by the site principal investigator or treating physician prior to the patient leaving the clinic

Visit 6/Week 28 (28 weeks +/- 4 days from baseline)

The following clinical and laboratory evaluations will occur 28 weeks after baseline with a +/- 4 day window.

- Interval medical and neurological history
- Vital signs
- Physical and neurological exam
- Laboratory assessments: CBC, Urinalysis, CMP
- MFIS, FSS, BDI-II, ESS, SF36, C-SSR*
- Protocol compliance study drug accountability
- Concomitant therapy and AEs
- Additional serum sample for research purposes

* The C-SSR must be reviewed by the site principal investigator or treating physician prior to the patient leaving the clinic

Premature termination visit

If discontinuation of study drug occurs, a premature termination visit must be performed as soon as possible, or within 7 days after the last dose of study drug. Randomized patients who were withdrawn from the study for any reason will not be replaced. The following clinical and laboratory evaluations will be performed:

- Interval medical and neurological history
- Vital signs

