- Physical and neurological exam
- Laboratory assessments: CBC, Urinalysis, CMP
- MFIS, FSS, BDI-II, ESS, SF36, C-SSR*
- Concomitant therapy and AEs

* The C-SSR must be reviewed by the site principal investigator or treating physician prior to the patient leaving the clinic

Unscheduled visits

Patients may be asked to return for unscheduled visit to assess any undesired clinical, or laboratory changes that occur during the study.

Study withdrawal

If a patient is lost to follow-up after all means of contact have been attempted, she/he will be withdrawn from the study.

Patient Monitoring and Evaluation

Patients will be instructed to contact their treating neurologist immediately in the event of a relapse.

A Stage 1 safety and efficacy analysis will be performed when 45th subject has completed visit 4(week 16). This analysis will be performed by the unblinded clinical and biostatistician members of the data safety monitoring board (DSMB). While this analysis is being performed, no new subjects may enroll in the investigation, but treatment of those already enrolled will continue while the analysis is taking place. If more subjects in the placebo arm demonstrate 20% or greater improvement than in the ACTH arm on both the MFIS and FSS, the study will be halted and subjects in the study will cease receiving investigational agents. If the ACTH arm is equal or superior to the placebo arm in MFIS and/or FSS, the study will continue, as will recruitment of the additional 45 subjects. If the study is halted due to lack of efficacy after the Stage 1 analysis, an additional analysis for efficacy will be performed utilizing those subjects who completed 6 months enrollment at the time the study was halted.

Treatment compliance

Patients will be instructed to complete a medication administration log and return the logs to study coordinator at each visit. Information on missed doses and total number of missed doses will be captured. Missing more than 2 doses in an 8-week interval is considered non-compliant. The investigator will discuss the medication regimen with non-compliant patients and they will be encouraged to continue with their injection schedule.

Potential Pitfalls and Contingencies

This study requires self-administration of an injectable agent. Thus there is a risk of non-compliance on the part of the subjects either due to needle phobia, intolerance to injections or lapse memory on the part of the subjects.

Data Processing and Analysis

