Data forms will be faxed to the data coordination center within 3 business days after each study visit and processed by staff trained in data entry procedures. The forms will be entered by two staff working independently. The completeness of the data and whether the data values are in an appropriate range will be checked periodically. Study sites will be asked to complete data clarification requests for confirmation of missing data or questionable information.

Statistical/Analytical Plan

Primary endpoint

Statistical analysis will be performed to test the change from baseline to end of study in two fatigue measures (MFIS and FSS) to be completed by patient at baseline, Week 8, Week 16, Week 24, and Week 28.

Secondary endpoint

Statistical analysis will be done to test the change from baseline to end of study in depression, sleepiness, and quality of life measures (BDI-II, ESS, and SF-36) to be completed by patient at baseline, Week 8, Week 16, Week 24, and Week 28.

All AEs are to be coded and grouped by organ system. AEs will also be tabulated by severity and by relationship and summarized by treatment group. Summary tables of the AEs will be presented to show the incidence and frequency by treatment group and by study site.

Statistical method

This study will collect longitudinal data that consists of repeated measures on each individual. The mixed-effects regression model for the analysis of longitudinal data will be used to test the changes of the fatigue scores over time.

Sample Size Justification

Ninety subjects will be recruited and randomized 1:1 to receive ACTH or placebo in a subject and examining physician-blinded manner. If the MFIS score decreases from 38 for about 20% with standard deviation =16.4 in the 45 patients who received ACTH, the power to reject the null hypothesis in a paired t-test with alpha=0.5 would be 86%. If the difference of the changes of MFIS score between two treatment group is 7.6 with within group standard deviation=16.4 in the 90 patients, the power to reject the null hypothesis in a t-test with alpha= 0.5 would be 87%. Ziemssen and colleagues (Ziemssen, Hoffman, Apfel, & Kern, 2008) studied the effect of glatiramer acetate on fatigue in MS patients. Glatiramer acetate was found to be associated with a reduction in absence from work and a significant reduction in fatigue symptoms, as measured by MFIS. The data from Ziemssen et al. were used for the sample size calculation for this study.

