D. REGULATORY, SAFETY AND MONITORING

Members and Responsibilities of DSMB

There will be 3 members of the DSMB, one will be a clinical neurologist with expertise in the treatment of patients with MS, one will be a PhD level biostatistician with past experience in statistical analysis of clinical studies of MS and one will be a physician with adequate expertise in endocrinology. The DSMB will review all adverse events (including all MS relapses) that occur during the study, independently conduct the interim analysis, the timing of which as described above, and the final analysis for safety and efficacy of the investigational treatment. The DSMB will also meet at any time they may choose if there are concerns for patient safety. Records of all committee reviews and input will be kept in the study binder.

Regulatory Requirements

The study will be performed in accordance with ICH GCP Guidelines and the Code of Federal Regulations for clinical research. Any amendments to the study protocol must be approved by Providence IRB and the IRB/IEC of each site before implementation. AEs and protocol violations or deviations must be reported according to the guideline of the IRB/IEC of each site.

Safety Assessments

Physical Examination

A full physical examination will be conducted at every visit. Any worsening or new abnormality that is clinically significant is to be recorded as an AE and will be analyzed as such. MS related symptoms are not to be reported as AEs unless, in the opinion of the investigator, the symptoms are unusually serious and relevant.

Vital Signs

Vital signs including body temperature, pulse, respiration rate, systolic and diastolic blood

pressure, and weight will be obtained at every visit

12-lead ECG

A 12-lead standard ECG will be performed at screening visit.

Clinical Laboratory Parameters

The following laboratory assessments will be performed at the local laboratory at selected visits:

- CBC
- Urinalysis
- CMP
- TSH
- Pregnancy Test (for female subjects only)

Adverse Event

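### After a Stage 1 lack-of-efficacy halt, the only efficacy analysis tied to the halt is restricted to six-month completers; the plan's mixed model on all randomised subjects should lead instead

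*Combined protocol and SAP*

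**What the plan says.** Section C, Patient Monitoring and Evaluation, sets a Stage 1 analysis for when the 45th subject completes Week 16. If the trial is then halted for lack of efficacy, study drug stops for everyone and an extra efficacy analysis is done "utilizing those subjects who completed 6 months enrollment at the time the study was halted". The protocol describes this analysis as additional.

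Two other statements bear on efficacy, and neither mentions a halt or names an analysis set:
- Statistical/Analytical Plan, Statistical method: "The mixed-effects regression model for the analysis of longitudinal data will be used to test the changes of the fatigue scores over time".
- Section D, Members and Responsibilities of DSMB: the board conducts "the final analysis for safety and efficacy of the investigational treatment".

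MFIS and FSS are scheduled at baseline and Weeks 8, 16, 24 and 28. They are also taken when study drug is discontinued: "a premature termination visit must be performed as soon as possible, or within 7 days after the last dose of study drug".

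The reasons for ending participation include "Patient has a relapse during the study", as well as adverse events and poor adherence.

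**The concern.** Having completed six months is a fact established after randomisation, so completers are not the groups that were randomised. The restriction removes two kinds of subject:

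- **Early stoppers.** Their removal is selection. It biases the comparison if stopping relates to response differently in the two arms. That is possible here: relapse ends participation, and Background and Rationale says that the ACTH dose "falls well within the range routinely employed, with efficacy, for treatment of MS relapses".
- **Subjects still in follow-up at the halt.** Their removal depends on entry date, so it mainly costs precision.

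Most subjects in both groups have a Week 8, Week 16 or termination-visit score that the prescribed analysis would not use. A reader also cannot tell which post-halt estimate is the main one, and that choice would be made after unblinded results exist. What is at stake is how a negative result is estimated and reported.

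**Working it through.** The plan gives no figure for this analysis, so there is none to reproduce. All sizes below rest on stated assumptions.

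**Inputs from the protocol.** 90 subjects, 1:1; difference 7.6 and SD 16.4 on MFIS (Sample Size Justification); Stage 1 at the 45th Week 16 visit; 20% dropout and 12-month accrual (Patient Recruitment); about 24 months of accrual from the dates in section E.

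**Assumed.** Uniform accrual; correlation between visits 0.4 to 0.8; the stopping mechanisms described below.

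**1. Patients omitted (before dropout).** The accrual rate r is 90/52.18 = 1.725 per week (12 months) or 90/104.36 = 0.862 (24 months). Stage 1 falls at week 45/r + 16 = 42.1 or 68.2. If enrolment runs until then, 45 + 16r = 72.6 or 58.8 are randomised. Those past Week 24 number 45 − 8r = 31.2 or 38.1.

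| Situation | 12 months | 24 months |
|---|---|---|
| 45 enrolled, immediate decision | 1 − 31.2/45 = 31% | 1 − 38.1/45 = 15% |
| Enrolment open to Stage 1, immediate decision | 1 − 31.2/72.6 = 57% | 1 − 38.1/58.8 = 35% |
| 45 enrolled, 8-week review | 0% | 0% |
| Enrolment open to Stage 1, 8-week review | 1 − 45/72.6 = 38% | 1 − 45/58.8 = 23% |

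In the 0% cells only early stoppers are left out. In every cell early stoppers come on top.

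**2. Precision (immediate decision).** For completers, the SE of the Week 24 difference is 16.4 × √(4/31.2) = 5.87 (12 months) or 16.4 × √(4/38.1) = 5.31 (24 months). Generalised least squares on all scheduled visits through Week 24, with compound symmetry at correlation 0.4/0.6/0.8, gives:

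| Situation | 12 months | 24 months |
|---|---|---|
| 45 enrolled | 5.66 / 5.45 / 5.19 | 5.22 / 5.13 / 5.02 |
| Enrolment open to Stage 1 | 5.58 / 5.26 / 4.83 | 5.17 / 5.01 / 4.81 |

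The completer variance, as the squared ratio of unrounded SEs, is therefore higher by 8–28% or 4–12% with 45 enrolled, and by 11–47% or 6–22% with open enrolment. Termination-visit scores are not counted.

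**3. Bias.** Let 20% stop in each arm after Week 8, with a probit model of slope b per SD of the change score. The mean shift among those who stay, in SD units of the driving score, is b/√(1+b²) × φ(0.8416)/0.8 = b/√(1+b²) × 0.35.

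- *Stopping driven by the unobserved Week 24 change, one arm only.* 16.4 × 0.35 × b/√(1+b²) gives 2.57, 4.06 and 5.13 points for b = 0.5, 1 and 2; simulation gave 2.6 to 5.2. The mixed model still carries 1.0 to 4.6, or 0.8 to 4.3 with a termination visit treated as Week 16.
- *Stopping driven by the observed Week 8 change, one arm only.* Multiply by the correlation: from 0.4 × 2.57 = 1.0 to 0.8 × 5.13 = 4.1. The mixed model's bias is about 0.
- *Both arms response-related, one with twice the slope.* Week 24-driven: for example 4.06 − 2.57 = 1.49, or 5.13 − 4.06 = 1.07; simulation gave about 1.0 to 1.6. Week 8-driven: about 0.4 × 1.07 = 0.4 to 0.8 × 1.49 = 1.2.
- *Both arms alike.* Zero. The sign otherwise depends on which arm stops selectively.

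**4. How often it matters.** In 60,000 simulated Stage 1 looks (22 versus 23 subjects, no dropout, assumed FSS change SD 11, baselines 48/46, MFIS–FSS correlation 0.6), a halt occurred in 2.8% at the planned effect, 10.9% at half of it and 27.5% with no effect.

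**The case against.** The strongest reply is that the plan largely covers this already. The completer analysis is additional, the mixed model and the board's final analysis are stated without condition, and a general plan need not be repeated for each contingency. That stands against one tempting inference: a reader might conclude that the mixed model is abandoned after a halt, and the documents do not say so. What remains is that neither analysis is said to lead after a halt or to include everyone randomised. The missing analysis set is a wider gap, which rewording this one sentence does not close for the unhalted trial.

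Other objections also hold in part:

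- **Scale.** The 57% and 5-point figures come from the least favourable assumptions. The reference to recruiting a further 45 against a total of 90 favours the 45-enrolled case. The protocol version is dated after the estimated end of enrolment, so accrual may have been slower than 24 months; at an assumed 36 months the omitted shares are 25% (open enrolment) and 10% (45 enrolled).
- **Mechanism.** Use of a dose to treat relapses does not show that it prevents them, and Background and Rationale says that this regimen is, to the authors' knowledge, new in MS. No stopping rates by arm are given. Differential stopping is possible, not shown.
- **Meaning of six months.** A reader might set "for the remainder of the 24 week participation" against "The proposed study is a 28-week randomized, placebo-controlled, double-blind trial" and call the term undefined. Background and Rationale uses six months for the treatment period, so Week 24 is the natural reading; naming the visit is only a clarification.
- **Data.** Subjects lost to follow-up may have no termination visit.
- **Consequence.** In the 12-month case the 95% half-widths are about 9.5 to 11.1 (mixed model) and 11.5 (completers). All exceed 7.6, so neither analysis is precise at the planned effect.

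None of this makes completers the better set to prescribe, since the alternative uses a model already in the plan and data already collected.

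**Conclusion.** The point holds as a cheap improvement of minor to moderate weight. The protocol sets a specific rule for the post-halt analysis, and that rule is inferior to its own mixed model applied to all randomised subjects. The loss of precision is modest in most settings. The bias runs from nothing to about 1.6 MFIS points when both arms stop alike or differ by a factor of two in strength; it reaches 5.2, against a planned effect of 7.6, only if selective stopping is confined to one arm. The mixed model removes the bias when stopping depends on observed scores and only reduces it otherwise.

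Accrual pattern, visit correlation and stopping mechanism are all assumed. The matter arises only after a halt, hence mainly when the treatment has little or no effect.

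**What to change.** Reword the post-halt sentence along these lines:

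> After a halt, efficacy will be analysed in all randomised subjects by assigned arm, with the mixed-effects model of the Statistical/Analytical Plan, using every available MFIS and FSS assessment up to and including the premature termination visit where one took place. Subjects who had completed the Week 24 visit by the halt form a sensitivity analysis.

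Fix in advance one rule for placing termination visits in time: either the actual time or the nearest scheduled visit. Naming Week 24 matches the six-month treatment period in Background and Rationale and the 24 weeks in Treatment Overview.

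The cost is slightly more analysis work and reliance on a missing-at-random assumption. No extra patients, visits or data are needed. No change to the stopping rule is proposed.

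### The primary analysis names neither the visit (Week 24 or Week 28) nor the treatment-by-visit term that would compare ACTH with placebo

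*Combined protocol and SAP*

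**What the plan says.** The primary analysis, in the Statistical/Analytical Plan of section C, reads: "Statistical analysis will be performed to test the change from baseline to end of study in two fatigue measures (MFIS and FSS". The sentence then lists assessments at baseline and Weeks 8, 16, 24 and 28, but does not say which of them is the end of study. The secondary analysis uses the same wording, to "test the change from baseline to end of study in depression, sleepiness, and quality of life measures".

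The only sentence on method is: "The mixed-effects regression model for the analysis of longitudinal data will be used to test the changes of the fatigue scores over time". It mentions no treatment term, interaction or contrast.

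Other sections bear on the visit:

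- Study Design: "The proposed study is a 28-week randomized, placebo-controlled, double-blind trial".
- The visit schedule ends with "Visit 6/Week 28 (28 weeks +/- 4 days from baseline".
- Laboratory Testing and Study Procedure puts Week 28 four weeks after the last dose.
- Section B describes six months of treatment and calls that a standard phase II trial duration. Treatment Overview speaks of 24 weeks of participation. Patient Monitoring and Evaluation bases the efficacy analysis after a Stage 1 halt on subjects with six months' enrolment.

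Other sections also bear on the comparison. Section B states the primary endpoint for patients who "fulfill the definition of PMSF when treated with ACTH compared to placebo". The objective under Endpoints is ACTH versus placebo. The second power statement begins "If the difference of the changes of MFIS score between two treatment group is 7.6". The first power statement is a paired test within the ACTH arm.

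**The concern.** Two statisticians following this plan could report different primary results. One could test Week 28 and the other Week 24. One could fit a treatment-by-visit contrast and the other a test of change over time.

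The two visits answer different questions. Week 24 is the end of dosing; Week 28 is a month off drug. Section B gives a reason to care about the on-drug period: the treatment length was chosen partly to show when effects begin and "whether they sustained over at least several months of medication use". If benefit fades after the last dose, a Week 28 test could miss it.

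A test of change over time that does not separate the arms cannot distinguish a drug effect from placebo response or regression to the mean. Regression to the mean is a live issue here, because patients enter on a high MFIS or FSS score.

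Early termination adds a further gap. MFIS and FSS are collected at a premature termination visit, due within 7 days of the last dose, and the plan does not say how those scores enter the analysis.

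**Working it through.** **Inputs.** From Sample Size Justification: between-group difference in MFIS change 7.6 (20% of 38), SD 16.4, 45 per arm. From Patient Recruitment: two-sided alpha 0.05. (Sample Size Justification prints alpha as 0.5; I use 0.05.) No week is attached to the 7.6.

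**1. The plan's own figures.** Power is from the noncentral t distribution.

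- Paired test, n = 45: SE = 16.4/√45 = 2.445; noncentrality = 7.6/2.445 = 3.109; power 86.0%. The stated 86% reproduces.
- Two-group test, 45 per arm: SE = 16.4 × √(2/45) = 3.457; noncentrality = 7.6/3.457 = 2.198; power 58.5%. The stated 87% does not reproduce. It does with 90 per arm (87.1%).

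The shortfall from 87% to 58% is a separate sample-size matter and has nothing to do with timing. It matters here only because 58% is the starting value in step 3.

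**2. What a literal test of change over time can do.** Suppose both arms improve by the same 3.8 points (an assumption, half of 7.6), so that there is no drug effect.

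- All 90 patients pooled: SE = 16.4/√90 = 1.729; 3.8/1.729 = 2.198; rejection probability 58.5%.
- One arm of 45: SE = 2.445; 3.8/2.445 = 1.554; rejection probability 33%.
- With a common change of 7.6 points, these become 99% and 86%.

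A treatment-by-visit contrast would reject 5% of the time in all of these cases.

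**3. What the choice of visit can do.** Let r be the share of the 7.6-point effect still present at Week 28. The documents give no carry-over figure, so r is an assumption. Noncentrality is 7.6r/3.457 at 45 per arm.

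| r | Effect | Noncentrality | Power |
|---|---|---|---|
| 1.00 | 7.6 | 2.198 | 58% |
| 0.75 | 5.7 | 1.649 | 37% |
| 0.50 | 3.8 | 1.099 | 19% |

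The first row also gives power at Week 24 under the full effect. With 36 per arm (45 less the plan's 20% dropout) the three values are 49%, 31% and 16%.

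**4. Which visit the text supports.** For Week 28: the stated trial length, the last scheduled visit and the last assessment listed in the analysis sentence. For Week 24: the 6-month treatment and trial-duration language, the 24-week participation wording and the six-month set for the post-halt analysis. Week 28 fits the words better, but neither reading is excluded.

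**The case against.** The strongest reply is that the intent is plain. The objective, the endpoint statement in section B and the second power statement all compare ACTH with placebo, so any competent analyst would fit the interaction. That stands as to intent. A reader might infer that the trial plans no comparison with placebo at all, and the documents do not support that. What is missing is the term in the model, and the paired power statement for the ACTH arm alone shows why it should not be left to inference.

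Second, Week 28 may be deliberate. The endpoint paragraph lists it, and the phrase about being treated with ACTH identifies the arm, not the measurement date. This also stands: the text does not establish that Week 28 is a mistake, or even that it is the chosen visit.

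Third, the power loss is hypothetical and comes from a single-visit t-test, whereas the plan specifies a longitudinal model. That is correct. A linear treatment-by-time slope (36 per arm; random intercept, residual SD 11.6) gives 66% or 51% power at 100% or 75% retention if onset is gradual, and 44% or 30% if the full effect is present from Week 8, against 49% for Week 24 alone. The direction depends on the shape of onset, which is itself a reason to name the contrast. It does not support a claim that power is lost by a known amount.

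Finally, the DSMB is unblinded and conducts the final analysis, so a reader might infer that the visit would be picked after seeing results. No section says so, and investigators stay blinded until study completion.

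**Conclusion.** The point holds as an ambiguity in the primary analysis that can change the result. The visit is unnamed, with Week 28 the better-supported reading and Week 24 a real alternative. The treatment-by-visit term is unstated although the comparison with placebo is clearly intended. The use of premature-termination scores is also unstated. The same wording carries over to BDI-II, ESS and SF-36.

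On size, a literal pooled test of change would reject about 58% of the time with no drug effect, given an assumed 3.8-point improvement in both arms. The fall in power from 58% to 37% or 19% is illustration only: it rests wholly on assumed retention of 75% or 50% at Week 28 and vanishes at full retention. The need to name the visit and the contrast does not depend on any of these figures.

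**What to change.** In the Statistical/Analytical Plan:

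1. Define the primary contrast as the ACTH-placebo difference in change from baseline to Week 24, from a mixed model with categorical visit, treatment, treatment-by-visit and the baseline score.
2. Report Week 28 as a secondary, off-drug follow-up.
3. Apply the same contrast to BDI-II, ESS and SF-36.
4. Enter premature-termination scores by their actual date within a pre-set visit window, and do not carry them forward to a later visit.
5. Have these choices fixed by staff who have not seen results by arm.

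If Week 28 is what the sponsor intends, the plan should say so and restate the aim as an effect that persists four weeks after dosing.

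The cost is one amendment, approved by the Providence IRB and each site's IRB/IEC as Regulatory Requirements provides. Week 24 and termination scores are already collected, so no visits or patients are added. The downside is that persistence after dosing becomes a secondary question.
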